lithotomy position and inverse insertion of ureteral catheter-guided puncture, a finding that pyonephrosis demanded the treatment of nephrostomy, channel bleeding that was required to maintain a nephrostomy tube, larger residual calculi that needed a nephrostomy tube for a secondary surgery, or a ureteral stone street that necessitated ureteroscopic lithotomy by changing to the lithotomy position; Or incomplete postoperative clinical data will be recorded by the study recruitment flow chart, but not included in the final data analysis.

11. Intervention measures: a. According to the randomization, the same associate chief urologist performed tubeless PCNL without reverse ureteral catheter or traditional reverse ureteral catheter; B. During the perioperative period, participants were given comprehensive blood biochemical examination and imaging evaluation, and antibiotics (second-generation cephalosporins or penicillins) were prophylactic. Participants with hypertension, diabetes and other comorbidities were given relevant drugs to control the tolerable level of surgery. C. Implementation process of tubeless PCNL without reverse insertion: After detaining urethral catheter for patients with tracheal intubation general anesthesia, to take a prone position, suffer renal biopsy under ultrasound guided look straight into the target under the calyces, syringe after water injection and suction is smooth, the guide wire guided by micro fascia dilator (Fr16 or Fr18) continuous build percutaneous renal channel expansion, step by step with holmium laser remove all break "can see the stone", A 6Fr double J tube was placed antegrade under the guidance of the guide wire, and no stone residue was detected. No active bleeding was observed in the channel during the withdrawal of the lens. The implementation process of traditional reverse insertion of tubeless PCNL was as follows: the participants were intubated for general anesthesia. First, the ureteral catheter was inserted under transurethral ureteroscopy in the lithotomy position and fixed on the catheter. The process of establishing percutaneous renal channel under ultrasound guidance and stone removal was the same as that of tubeless PCNL without the use of a retro-inserted ureteral catheter. Double J tubes were placed antegrade under the guidance of guide wire, and the

skin incision was sutured and closed after no residual "visible stones" and no active bleeding under endoscopic observation.

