12. Outcome measures: The primary clinical end point was the incidence of postoperative complications (including postoperative fever, bleeding, pain, and changes in renal function; Ureterostone street was formed after operation. Air - fluid chest after operation); The secondary clinical end points were operation time, hospital stay, hospital cost and stone clearance rate.

13. Recruitment flow chart:

14. Sample size: Combined with the number of outpatient calculi patients and the number of PCNL surgeries in our department of Urology each year, we planned to initially include 200 patients with renal and/or upper ureteral calculi who underwent tubular PCNL surgery in our hospital from October 2022 to December 2024, and randomly assigned at 1:1.

15. Participants: Patients with upper urinary stones attending the Urology Clinic of the First Affiliated Hospital of the University of South China were recruited.

16. Allocation sequence generation, allocation hiding, implementation methods: Computer random number generator was used. Participants with odd numbers were assigned to experimental group, where they underwent tubeless PCNL without

reverse insertion of a ureteral cathete. Participants with even numbers were assigned to control group and underwent tubeless PCNL with reverse insertion of a ureteral cathete. This process takes place in the operating room.

17. Blinding: In a single-blind approach, patients are told to participate in a clinical trial but are not informed about the specific intervention, while the person administering the intervention is clearly informed.

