18. Data collection: The measured data of all the required: 1. The demographic data, stone characteristics and preoperative baseline data, including the proportion of gender, age, body mass index (BMI) and basic diseases distribution, location, stones, stone maximum cross-sectional area, the longest diameter antler shape proportion and pelvic effusion width, partial side and puncture operation, etc. 2. Data of the main end points included: Postoperative fever and inflammation (temperature, preoperative blood leukocyte count difference after operation, neutrophils ratio difference, post-operative sepsis), postoperative bleeding (preoperative differential postoperative hemoglobin and hematocrit value and blood in the urine, subcapsular renal week or hematoma after operation, postoperative DSA guided by selective renal artery embolization bleeding), postoperative pain, postoperative analgesia drug demand, Mainly non-steroidal anti-inflammatory analgesic drugs), renal function changes (preoperative and postoperative serum creatinine difference), ureteral stone street formation rate and the incidence of gas and fluid chest (postoperative CT showed the presence of gas and fluid accumulation in the chest); Secondary end points included operation duration, length of hospital stay, hospitalization cost, and stone clearance rate. 3. Follow-up was conducted for 1 month after discharge, including: high fever, obvious pain and hematuria after discharge; Whether there is readmission; Whether to remove the double J tube as scheduled.

19. Statistical analysis plan: SPSS26.0 statistical software was used for analysis. Measurement data were expressed as mean  $\pm$  standard deviation ( $X \pm S$ ) and t-test was used. Enumeration data were expressed as frequency and percentage by  $X^2$  or Fisher exact test. Rank sum test was used for rank data.  $P < 0.05$  was considered

statistically significant.

20. Ethical approval: This trial was a human life science and medical study and was approved by the Medical Ethics Committee of the First Affiliated Hospital of the University of South China (No. : 2022110924001).

21. Informed consent: All participants enrolled in the study signed a surgical consent and a clinical trial informed consent to collect and use the medical behavior information and biological samples for the study.

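### Transfusion is missing from the bleeding data in section 18, and the postoperative sample is not tied to a time before it, so the haemoglobin and haematocrit fall, and possibly the bleeding incidence, can be understated

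*Protocol*

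**What the plan says.** Section 12 sets the primary end point as the incidence of postoperative complications, "including postoperative fever, bleeding, pain, and changes in renal function" among them. It gives no threshold for a bleeding event.

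Section 18 lists the data behind each component. For bleeding these are:

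- the change in two laboratory values, plus haematuria: "postoperative bleeding (preoperative differential postoperative hemoglobin and hematocrit value and blood in the urine";
- two events: "subcapsular renal week or hematoma after operation, postoperative DSA guided by selective renal artery embolization bleeding". The translation is rough, but the sense is perirenal or subcapsular haematoma and embolisation under angiography.

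The items collected in the month after discharge include "high fever, obvious pain and hematuria after discharge", readmission and removal of the double J tube. Transfusion is not among them and appears nowhere else in the protocol. No time is given for the postoperative blood sample.

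For measurement data, section 19 gives mean and standard deviation "and t-test was used". It has no provision for a value altered by treatment.

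**The concern.** Transfusion raises both haemoglobin and haematocrit. When it comes before the postoperative sample, the recorded fall is the true fall less the rise from transfusion. Both laboratory measures err in the same direction, so one cannot correct the other, and the error falls on patients who bled enough to be transfused.

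The events in the list do not fully close the gap. A transfused patient with no haematoma and no embolisation is marked only by a blunted laboratory change and perhaps by blood in the urine. Haematuria is not graded, so that entry looks the same as trivial haematuria.

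Safety is part of the trial's stated objective. If one arm bleeds more and is transfused more, the observed difference in mean fall is pulled towards zero. If the arms are transfused equally, the mean difference is unaffected on average, but blood loss is understated in both.

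**Working it through.** **No figure to reproduce.** The sample size in section 14 rests on patient volume ("we planned to initially include 200 patients with renal and/or upper ureteral calculi", allocated 1:1). No rate, SD, effect size or power is given. The check is therefore a reading of the whole protocol for transfusion, which found none, followed by an illustration.

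**Inputs**

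| Input | Value | Source |
|---|---|---|
| Patients per arm | 100 | section 14, 200 allocated 1:1 |
| Significance level | 0.05, taken as two-sided | section 19; sidedness assumed |
| Transfused share, two arms | 2% v 6% (also 1% v 5%, 3% v 10%) | assumed |
| Rise in haemoglobin from transfusion | 10 or 20 g/L (40 as an extreme) | assumed |
| SD of haemoglobin fall | 10 g/L | assumed |
| Timing | every transfusion precedes the sample | assumed, worst case |

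**Loss in the arm difference.** Loss = (difference in transfused share) × (rise).

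| Shares | Rise 10 | Rise 20 | Rise 40 |
|---|---|---|---|
| 2% v 6% | 0.04 × 10 = 0.4 g/L | 0.04 × 20 = 0.8 | 0.04 × 40 = 1.6 |
| 1% v 5% | 0.4 | 0.8 | 1.6 |
| 3% v 10% | 0.7 | 1.4 | 2.8 |

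If only half of the transfusions preceded the sample, equally in both arms, each figure would halve: 2% v 6% would give 0.2 to 0.4 g/L for a rise of 10 to 20.

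**Yardstick for the t-test.** Standard error of the difference = SD × √(2/100) = 10 × 0.1414 = 1.4 g/L. Difference detectable with 80% power = (1.96 + 0.84) × 1.414 ≈ 4.0 g/L, or about 0.40 SD. The loss of 0.4 to 0.8 g/L is between 0.4/1.4 ≈ 0.3 and 0.8/1.4 ≈ 0.6 of a standard error.

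**Loss in a single arm mean.** Loss = transfused share × rise. It runs from 0.01 × 10 = 0.1 g/L to 0.10 × 40 = 4.0 g/L.

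**Effect on individual patients.** Take the true fall as lognormal with mean 12 and SD 10 g/L, and suppose that the heaviest-bleeding 5% are transfused (all assumed; simulated). Their true mean fall is 43 g/L.

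| Rise (g/L) | Their recorded mean fall (g/L) | Share of them recorded below the average fall of 12 |
|---|---|---|
| 10 | 33 | 0% |
| 20 | 23 | 13% |
| 40 | 3 | 83% |

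**Events.** Transfusion in 2 of 100 against 6 of 100 gives a Fisher exact p of 0.28. Recording it would describe serious bleeding properly, but would probably not produce a significant difference by itself.

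**The case against.** The strongest reply is that the gap is narrow. Haemoglobin change is only one of several bleeding items. Haematoma and embolisation mark serious bleeds directly, and many heavy bleeders will have one of them. To lose its marking as a serious bleed, a case must involve transfusion but no haematoma and no embolisation. To mask the fall, the transfusion must also precede the sample. Section 10 narrows the group further: it excludes abnormal coagulation, and it drops from the final analysis any "channel bleeding that was required to maintain a nephrostomy tube". The primary end point is an incidence, and with no haemoglobin threshold a blunted fall changes that incidence only under a cut-off that the protocol does not state. Sampling windows and the handling of transfused patients may be left to a statistical analysis plan, and transfusion could be retrieved from the chart.

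Most of this stands, and it limits the claim. Three stronger conclusions that a reader might draw are not supported:

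- *Bleeding is judged by the laboratory change alone, so the worst bleeders disappear.* Section 18 also lists haematuria, haematoma and embolisation.
- *A large fraction of the bleeding difference is lost.* A large fraction appears only if the loss is expressed as a share of the transfused patients' own contribution. Against the precision of the whole comparison it is modest.
- *A difference in serious bleeding would go entirely unrecorded.* That is true of transfusion as an event, but not of bleeds that also show as haematoma, embolisation or blood in the urine.

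The reply does not remove the point. Section 18 is the protocol's own list of what is measured, and it is specific enough to name embolisation. An analysis plan can handle transfusion only if transfusion and its timing have been collected. Without either time, nobody can tell which recorded falls are affected. Dropping bleeders who need a nephrostomy tube is a separate problem. It pushes the bleeding outcome the same way and does not excuse this one.

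**Conclusion.** The point holds in a limited form. As written, the plan understates the haemoglobin and haematocrit fall of anyone transfused before the postoperative sample. It also fails to mark as serious a transfused bleed without haematoma or embolisation. The bleeding incidence may be understated too, but by how much depends on a definition of bleeding that section 12 does not give.

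The size cannot be known from the protocol. With 2% v 6% transfused and a rise of 10 to 20 g/L, the arm difference in mean fall shrinks by about 0.4 to 0.8 g/L, well under one standard error of 1.4 g/L at an assumed SD of 10. Only the extreme corner of the assumed range (3% v 10%, rise 40, loss 2.8 g/L) reaches two standard errors. The effect is large for the individual patient and modest for the t-test. The change should be made because it corrects a safety measure within the primary end point at little cost. The trial's conclusion is not shown to turn on it.

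**What to change.** In section 18, add transfusion to the bleeding items: yes/no, units, date and time, and indication. In section 12, count transfusion given for bleeding as a bleeding complication; recording the indication keeps out transfusions given for other reasons.

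Define the postoperative haemoglobin and haematocrit as a value taken in a fixed window before any transfusion, with the window stated in advance. As a sensitivity analysis, compare the arms by ranks with patients transfused for bleeding placed worst. This also keeps in transfused patients who have no pre-transfusion sample. Section 19 already provides a rank sum test, so no new method is needed. Adding back an assumed rise per unit is not recommended, because the protocol has no figure for it.

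The cost is one more entry from the existing chart and a few sentences of protocol text. The downside is that the recorded value will depend slightly on when blood is drawn, which the fixed window limits. The change concerns recording and analysis only and sets no rule for when to transfuse.

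### Five laboratory changes are compared by unadjusted t-test, although adjusting for the preoperative value already collected is, in large samples, never less precise

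*Protocol*

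**What the plan says.** Section 18 of the protocol sets out the data behind the main end points. Five of the items are laboratory changes from before to after surgery:

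- two for inflammation: "preoperative blood leukocyte count difference after operation, neutrophils ratio difference"
- two for bleeding: "preoperative differential postoperative hemoglobin and hematocrit value"
- one for kidney function: "renal function changes (preoperative and postoperative serum creatinine difference"

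Section 19, which is headed as the statistical analysis plan, summarises measurement data by mean and standard deviation, "and t-test was used". It names no covariate for any analysis.

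Three other places bear on the point. Section 12 states that "The primary clinical end point was the incidence of postoperative complications". Section 14 derives the sample size from the clinic's caseload: "we planned to initially include 200 patients", randomised 1:1. Section 10 says that patients with certain intraoperative events or incomplete postoperative data are recorded in the flow chart "but not included in the final data analysis".

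**The concern.** Comparing change scores by t-test amounts to fixing the slope of the postoperative on the preoperative value at 1. If the true slope differs from 1, the subtraction removes too much or too little of the baseline, and the excess variation stays in the comparison. ANCOVA estimates the slope instead of fixing it. The preoperative value must exist for every patient whose difference is computed, so the adjustment needs no new data.

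What is at stake is precision, not bias. The 200 patients were not chosen to give any stated power, and the exclusions in section 10 may reduce the number analysed. For these five measures, baseline adjustment can gain precision without more patients. It does nothing to repair the exclusions, which affect either analysis alike.

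**Working it through.** **Inputs from the protocol.** Five change scores (section 18); t-test, significance at P < 0.05 (section 19, taken as two-sided); 200 patients at 1:1, so about 100 per arm (section 14). The figure of 200 cannot be reproduced, because no effect size, SD or power is given.

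**Inputs assumed.** The pre-post correlation ρ and the ratio k of postoperative to preoperative SD are not in the protocol, so both are varied.

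**Formulas.** Set the preoperative SD to 1. Per patient:

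- variance for the change score: 1 + k² − 2ρk
- residual variance for ANCOVA: k²(1 − ρ²)
- first minus second: 1 − 2ρk + ρ²k² = (1 − ρk)²

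The last line is never negative and is zero only when the slope ρk equals 1. So in large samples ANCOVA is never the less precise method. Let R be the ANCOVA variance divided by the change-score variance. With k = 1, R = (1 + ρ)/2.

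**Worked cases.**

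- k = 1, ρ = 0.5: change 1 + 1 − 1 = 1; ANCOVA 0.75; R = 0.75.
- k = 0.8, ρ = 0.5: change 1 + 0.64 − 0.8 = 0.84; ANCOVA 0.64 × 0.75 = 0.48; R = 0.57.
- k = 1.25, ρ = 0.8 (slope 1): change 1 + 1.5625 − 2 = 0.5625; ANCOVA 1.5625 × 0.36 = 0.5625; R = 1.00, no gain.

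**Variance ratio R over the assumed range.**

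| SD ratio k | ρ 0.3 | ρ 0.5 | ρ 0.7 | ρ 0.8 | ρ 0.9 |
|---|---|---|---|---|---|
| 0.8 | 0.50 | 0.57 | 0.63 | 0.64 | 0.61 |
| 1 | 0.65 | 0.75 | 0.85 | 0.90 | 0.95 |
| 1.25 | 0.78 | 0.89 | 0.98 | 1.00 | 0.95 |
| 1.5 | 0.87 | 0.96 | 1.00 | 0.95 | 0.78 |

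**What this means with equal SDs (k = 1).** The confidence interval width is multiplied by √R. For a comparison in which the t-test would have a hypothetical 80% power, ANCOVA has power Φ(2.80/√R − 1.96). The precision that the t-test gets from 200 patients needs 200 × R patients with ANCOVA.

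| ρ | R | CI narrower by | power instead of 80% | patients for equal precision |
|---|---|---|---|---|
| 0.3 | 0.65 | 19% | 93% | 130 |
| 0.5 | 0.75 | 13% | 90% | 150 |
| 0.7 | 0.85 | 8% | 86% | 170 |
| 0.8 | 0.90 | 5% | 84% | 180 |
| 0.9 | 0.95 | 3% | 82% | 190 |

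**Cost of estimating the slope.** The finite-sample variance factor is 1 + 1/(N − 4). At N = 200 it is 1 + 1/196 = 1.0051. At N = 160 (20% excluded, an assumption) it is 1 + 1/156 = 1.0064.

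**Simulation check.** In 20,000 simulated trials with 100 per arm and k = 1, R was 0.64, 0.75, 0.85, 0.90 and 0.95 for the five correlations. With k = 1.25 and ρ = 0.8 it was 1.005, the finite-sample cost alone. In a separate set of 4,000 trials per scenario, including skewed baselines and slopes that differed by arm, the type I error of the change-score t-test lay between 4.4% and 5.3%. This confirms that the planned test is valid.

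The t-test's sensitivity to chance baseline imbalance is this same loss of precision seen from another side. It should not be counted twice.

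**The case against.** The strongest reply is that nothing here is an error. The t-test is valid, the gain may be zero, and covariate adjustment is often left to a separate SAP. Section 19 assigns tests by type of data and never states in so many words that arms are compared on change scores. The stated primary end point is an incidence, which this change does not touch. No effect size or decision rule is attached to the five laboratory measures. The size of the gain is wholly assumed, and with equal SDs and correlations of 0.8 to 0.9 it is only a 3% to 5% narrower interval.

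Most of this stands as a limit on the weight of the point. It is about efficiency, and the benefit cannot be quantified from the protocol. It does not remove the point, for two reasons. First, section 19 is presented as the statistical analysis plan and names the t-test for measurement data. Together with the differences listed in section 18, the unadjusted comparison of changes is the natural reading, and a separate SAP would have to depart from it to adjust. Second, the possible gain and the possible loss are very unequal: up to half the variance in the range considered, against about half a percent.

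**Conclusion.** The concern holds as a matter of efficiency. The planned t-test on the five laboratory differences is valid, but in large samples it is never more precise than ANCOVA on the preoperative value, and it is equal only at a slope of exactly 1. Over assumed SD ratios of 0.8 to 1.5 and correlations of 0.3 to 0.9, the variance ratio runs from 0.50 to 1.00, which is a large gain at one end and none at the other. These figures rest on linear-model variance formulas and on correlations and SDs that the protocol does not supply. The change is recommended because it costs almost nothing. No conclusion about the section 12 incidence end point depends on it.

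**What to change.** Add to section 19:

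> For leukocyte count, neutrophil ratio, haemoglobin, haematocrit and serum creatinine, the arms are compared by analysis of covariance with the postoperative value as outcome, allocated arm as factor and the preoperative value of the same measure as covariate; the adjusted mean difference is reported with its 95% CI.

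This replaces the t-test for these five measures only. The unadjusted mean change can still be reported by arm as a description, and the incidence comparison stays as it is. Naming the covariate in advance also removes any later choice between adjusted and unadjusted results.

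The cost is one sentence and one degree of freedom per model. No new data are needed, and the method is a standard linear model.
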